1.3 Schedule of Events

SoE Quick Link	Table Title
Table 1	Schedule of Events – Schedule A (Q3W Dosing)
Table 2	Schedule of Events – Schedule B (D1 & D8 Dosing)
Table 3	Schedule of Events – Schedule A (Q3W Dosing) if Step-Dosing is Implemented
Table 4	Schedule of Events – Schedule B (D1 & D8 Dosing) if Step-Dosing is Implemented

Table 1 Schedule of Events – Schedule A (Q3W Dosing)

Treatment Visit Window	SCR ^a	Treatment Period ^b (21-day cycles)									EOT ^c	RFU	LTFU ^e	Notes
		Cycle 1				Cycle 2				Cycle 3+				
		D1	D2	D4	D8	D1	D2	D4	D8	D1				
		0	0	0	±1	±3	0	0	±1	±3				
General and Safety Assessments														
Informed consent	X													
Eligibility criteria	X													
Demography	X													
Medical history	X													
Physical examination	X	(X)			X	X				X	X			Full physical exam at screening and end of treatment; brief physical exam at all other time points (ie, C1D8 and CXD1). (X): Not required if completed within 7 days of Day 1.
Height	X													
Weight	X	X			X	X				X	X			Dose adjustment required if weight changes $\geq 10\%$ from weight used for C1D1 dose (recorded at screening or C1D1 visit or per institutional standard).
Vital signs	X	X	X		X	X				X	X			All D1 assessments include a pre-dose (within 1 h prior to dose) and a post-dose assessment 1h after EOI (± 15 min). Measured in a semi-supine position after 5 min rest.
12-lead ECG	X	(X)			X						X			(X): Completed 6-24 hours after EOI
ECHO	X													If ECHO is not available or appropriate according to the institutional standard, then multi-gated acquisition (MUGA) scan is permitted
PFTs	X													
ECOG performance status	X	(X)			X					X	X			Must be confirmed per Section 8 before dosing C1D1 (X): Assessment can be performed within 48 hours prior to dosing
Hospitalization		X												24-hour hospitalization (may be extended per Investigator discretion). Patients should be advised to stay within a reasonable distance of the clinical site for the first week after the first dose.

	SCR ^a	Treatment Period ^b (21-day cycles)									EOT ^c	RFU	LTFU ^e	Notes	
		Cycle 1				Cycle 2				Cycle 3+					
		D1	D2	D4	D8	D1	D2	D4	D8	D1					
Treatment Visit Window		0	0	0	±1	±3	0	0	±1	±3					
AE review	(X)	←-----→												(X): Only collect AEs related to study-mandated procedures during screening period.	

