AE = adverse event; CR = complete response; CT = computed tomography; CXDX = cycle X day X; D = day; ECG = electrocardiogram; ECHO = echocardiogram; ECOG = Eastern Cooperative Oncology Group; EOI = end of infusion; EOT = end of treatment; iRECIST = Response Evaluation Criteria in Solid Tumors for use in cancer immunotherapy trials; LTFU = long-term follow-up; M = month; MRI = magnetic resonance imaging; PD = progressive disease; PDn = pharmacodynamic(s); PD-L1 = programmed cell death ligand 1; PFTs = pulmonary function tests; PR = partial response; Q3W = every 3 weeks; RECIST = Response Evaluation Criteria in Solid Tumors; RFU = radiological follow-up; SAE = serious adverse event; SCR = screening; WOCBP = women of child bearing potential

- a The screening period is up to 28 days prior Cycle 1 Day 1.
- b All assessments should be performed pre-dose of NL-201 or pembrolizumab, if applicable unless otherwise indicated.
- c Upon permanent discontinuation of study drug for any reason, an end of treatment visit should be scheduled as soon as possible but within 30 days following cessation of study treatment or before patient initiates new anti-cancer therapy, whichever is earlier.
- d For Parts 1 and 3 (Dose Escalation), if study treatment is discontinued for reasons other than death, withdrawal of consent, lost to follow-up, or study closure, a CT scan should be performed at EOT visit (within + 2 weeks) if a post-baseline CT scan has not been performed within 5 weeks prior to the EOT visit.
- e Long-term follow-up assessments occur every 6 months (± 1 month) until death, withdrawal of consent, lost to follow-up, or study closure, whichever occurs first, for a maximum of 2 years after end of treatment. This visit can occur by telephone.

Table 2 Schedule of Events – Schedule B (D1 & D8 Dosing)

	SCR ^a	Treatment Period ^b (21-day cycles)												EOT ^c	RFU	LTFU ^e	Notes
		Cycle 1						Cycle 2				Cycle 3+					
		D1	D2	D4	D8	D9	D11	D1	D2	D4	D8	D1	D8				
Treatment Visit Window		0	0	0	±1	0	0	±3	0	0	±1	±3	±1				
General and Safety Assessments																	
Informed consent	X																
Eligibility criteria	X																
Demography	X																
Medical history	X																
Physical examination	X	(X)			X			X			X	X		X			Full physical exam at screening and end of treatment; brief physical exam at all other time points (ie, C1D8, C2D8, and CXD1). (X): Not required if completed within 7 days of Day 1.
Height	X																

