In addition, there will be backfill cohorts (up to approximately 12 patients in total) , at certain DMC-cleared dose levels and schedules, to collect, pharmacokinetic, pharmacodynamic and response data in certain tumor types or to explore additional pre-medication regimens (eg. steroids). These patients will not be part of the DLT evaluation but will be included in the safety population.

Refer to [Section 6.2.1](#) for details regarding dose escalation. The final decision in terms of the dose to be applied to the next set of $n \geq 3$ patients will be made by the DMC based upon the mTPI design together with the available safety and laboratory data.

Based on the totality of data arising in Part 1, the DMC will determine a RP2D. If the RP2D requires step-dosing, the step-dosing regimen would be incorporated into dosing for patients in Part 2.

Part 2: Monotherapy Dose Expansion Study of NL-201

This monotherapy dose expansion cohort study will evaluate safety and estimate antitumor activity of NL-201 as monotherapy in diseases that are responsive to IL-2, ie, (1) malignant melanoma and (2) RCC. The RP2D (and treatment schedule) for these cohorts will be determined in Part 1.

Expansion cohorts will individually comprise up to 30 patients each, of which a minimum of 8 patients per cohort will be required to have paired biopsies of the same lesion before and after treatment with NL-201. Pre-treatment biopsies will occur up to 28 days prior to the first dose (Cycle 1 Day 1), while post-treatment biopsies will occur 7 (\pm 2) days after the Cycle 2 dose.

Part 3: Dose Escalation Study of NL-201 in Combination with Pembrolizumab

Dose escalation will follow a mTPI design to guide dose escalation and de-escalation within each schedule. NL-201 will be administered as an IV infusion in 21-day cycles in cohorts of $n \geq 3$ patients at a time. The starting dose of NL-201 will be at least 1 dose level below the highest dose level that has been recommended as safe and tolerable by DMC from Part 1 of the study.

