6.1 Study Drug(s) Administered

6.1.1 Investigational Products

Table 7 Investigational Products: NL-201 and Pembrolizumab

Intervention Name	NL-201	Pembrolizumab (Parts 3 and 4 only)
Type	Biologic	
Dose Formulation	Solution for infusion	Solution for infusion
Unit Dose Strength(s)		100 mg/vial
Dosage Level(s)	See Table 8 and Table 9	200 mg Q3W
Route of Administration	IV infusion	IV infusion
Dosing Instructions	NL-201 will be dosed as per the Pharmacy Instructions. IV dosing will occur either every 21 days (for Schedule A) or on Days 1 and 8 of every 21-day cycle (for Schedule B). For IV: patients that weigh ≥ 100 kg, the dose is capped as to not allow more than 100 times the current dose level to be administered to a patient at 1 time (see Table 8 and Table 9). Parts 3 and 4 only: NL-201 to be administered 30-60 minutes post administration of pembrolizumab.	Pembrolizumab will be administered using IV infusion on Day 1 of each 21-day cycle after all procedures and assessments have been completed. Pembrolizumab will be administered as a dose of 200 mg using a 30-minute IV infusion. Sites should make every effort to target infusion timing to be as close to 30 minutes as possible. However, given the variability of infusion pumps from site to site, a window between -5 minutes and +10 minutes is permitted (ie, infusion time is 30 minutes (-5 min/+10 min). After Cycle 1 trial treatment of pembrolizumab may be administered up to 3 days before or after the scheduled Day 1 of each cycle due to administrative reasons, however, pembrolizumab must always be administered on the same day as NL-201 when used in combination. The Pharmacy Manual contains specific instructions for the preparation of the pembrolizumab infusion and administration of infusion solution.
Hospitalization Guidance	Patients will remain in a hospital setting for the first 24 hours after completion of their first dose (IV) on study (may be extended per Investigator discretion), and for 8 hours after receiving subsequent doses. This period of hospital observation will be reduced to 2 hours for patients that have tolerated 3 consecutive doses. Required monitoring times may be adjusted by Neoleukin and/or per DMC recommendation pending review of safety data. Patients should also be advised to stay within a reasonable distance of the clinical site for the first week after the first dose.	
Use	Investigational	
Sourcing	Provided centrally by the Sponsor.	

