6.2.1.2 Part 3: Dose Escalation Study of NL-201 in Combination with Pembrolizumab

In Part 3, an mTPI²⁵ will be used to guide dose escalation and de-escalation for NL-201 within each schedule, with the final decision regarding dose assignment being made by the DMC. In Schedule A, patients will be dosed every 21 days, while in Schedule B patients will be dosed on Days 1 and 8 of every 21day cycle. The mTPI design matrix is shown in Figure 6.

Figure 6 mTPI Design Matrix for Part 3

Number of DLT	Number of enrollment at current dose level													
	2	3	4	5	6	7	8	9	10	11	12	13	14	15
0	E	E	E	E	E	E	E	E	E	E	E	E	E	E
1	S	S	S	S	E	E	E	E	E	E	E	E	E	E
2	DU	D	S	S	S	S	S	S	S	E	E	E	E	E
3		DU	DU	D	S	S	S	S	S	S	S	S	S	S
4			DU	DU	DU	D	D	S	S	S	S	S	S	S
5				DU	DU	DU	DU	DU	D	S	S	S	S	S
6					DU	DU	DU	DU	DU	DU	D	S	S	S
7						DU	DU	DU	DU	DU	DU	DU	D	D
8							DU	DU	DU	DU	DU	DU	DU	DU
9								DU	DU	DU	DU	DU	DU	DU
10									DU	DU	DU	DU	DU	DU
11										DU	DU	DU	DU	DU
12											DU	DU	DU	DU
13												DU	DU	DU
14													DU	DU
15														DU

D = De-escalate to the next lower dose; DLT = dose limiting toxicity; DU = current dose is unacceptably toxic;
 E = Escalate to the next higher dose; mTPI = modified toxicity probability interval; S = stay at the current dose
 Target toxicity rate = 30%
 Flat noninformative prior Beta (1,1) is used as a prior and $\varepsilon_1 = \varepsilon_2 = 0.03$

Assessment of toxicity and dose escalations or de-escalation as guided per the mTPI will be made on an ongoing basis based upon DLT-evaluable patients as defined by occurrence of DLT or completion of 21 days on study, and after review by the DMC. If dose escalation is indicated per mTPI, the DMC will recommend escalation to the next planned dose or to an intermediate dose based on review of observed toxicity. Dose escalation and de-escalation will occur independently for Schedules A and B, and a given dose level must be determined by the DMC to be safe on Schedule A prior to enrolling on Schedule B. Dose levels will be escalated more gradually at higher dose levels (see [Table 9](#) for a proposed dose escalation scheme).

Table 9 Sample Dose Escalation Scheme for Part 3

Combination Cohorts (21-day cycles)				Maximum dose of NL-201 that may be administered at 1 time (μg) ^a
Schedule A (D1)	Schedule B (D1+D8)	Pembrolizumab (D1)	NL-201 dose level ($\mu\text{g}/\text{kg}$)	
Planned NL-201 Dose Level				
P-1A	P-1B	200 mg	0.3	30
P-2A	P-2B	200 mg	1	100
P-3A	P-3B	200 mg	3	300

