6.2.1.3 Dose-Limiting Toxicity

Part 1

DLT must occur within Cycle 1 (< 21 days from first dose), or prior to completion of 21 days after first administration of NL-201 or after reaching the cohort target dose (CTD) in patients receiving step-dosing (see Appendix 1 [[Section 10.1](#)]). DLT is defined by the following:

- Any death not clearly due to the underlying disease or extraneous causes
- Hy's law:
 - AST/ALT > 3 × ULN, and
 - TBL > 2 × ULN, and
 - Alkaline phosphatase < 2 × ULN without alternative etiology
 - No other reason can be found to explain the combination of increased ALT/AST and TBL, such as viral hepatitis A, B, or C; preexisting or acute liver disease; or another drug capable of causing the observed hepatocellular injury
- Neutropenic fever
- ≥ Grade 4 neutropenia or thrombocytopenia > 5 days
- ≥ Grade 3 thrombocytopenia with bleeding
- ≥ Grade 4 vomiting/diarrhea of any duration
- ≥ Grade 3 autoimmune disorder. Examples include, but are not limited to, treatment-emergent myasthenia gravis, toxic thyroiditis, bullous pemphigoid, and Stevens-Johnson Syndrome
- ≥ Grade 3 fatigue ≥ 1 week
- ≥ Grade 3 electrolyte abnormalities that lasts > 72 hours or are symptomatic
- ≥ Grade 3 lipase and amylase if associated with symptoms of pancreatitis
- ≥ Grade 3 AST or ALT elevation lasting ≥ 14 days
- Any other ≥ Grade 3 non-hematologic toxicity that is at least possibly related to the study drug

- Recurrent Grade 3 infusion-related reaction despite pre-medication, or Grade 4 infusion-related reaction on the first occurrence
- Dose delay of > 14 days for the study drug due to an AE

All AEs of the specified grades will be considered DLTs except those that are clearly and incontrovertibly due to disease progression or extraneous causes.

Part 3

All toxicities will be graded using Common Terminology Criteria for Adverse Events (CTCAE) Version 5.0 based on the investigator assessment. The DLT window of observation will be during Cycle 1.

The occurrence of any of the following toxicities during Cycle 1 will be considered a DLT, if assessed by the investigator to be possibly, probably, or definitely related to study treatment administration.

- Grade 4 nonhematologic toxicity (not laboratory).
- Grade 4 hematologic toxicity lasting ≥ 7 days, except thrombocytopenia:
 - Grade 4 thrombocytopenia of any duration
 - Grade 3 thrombocytopenia associated with clinically significant bleeding

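### In Parts 1 and 3 without step-dosing, the ±3-day window at Cycle 2 Day 1 allows the next dose on Days 19–21, inside the 21-day DLT period, so its toxicity can be scored against the Cycle 1 regimen

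*Combined protocol and SAP*

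**What the plan says.** **Visit windows (Section 1.3).** Without step-dosing, the Table 1 row for Schedule A is "Treatment Visit Window 0 0 0 ±1 ±3 0 0 ±1 ±3" and the Table 2 row for Schedule B is "Treatment Visit Window 0 0 0 ±1 0 0 ±3 0 0 ±1 ±3 ±1". Cycle 2 Day 1 is the fifth entry in the first row and the seventh in the second; both are ±3. The tables serve all four parts.

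**Pembrolizumab (Section 6.1.1, Table 7).** After Cycle 1, "pembrolizumab may be administered up to 3 days before or after the scheduled Day 1 of each cycle due to administrative reasons". The same cell adds that "pembrolizumab must always be administered on the same day as NL-201 when used in combination", so in Part 3 an early pembrolizumab dose brings NL-201 forward with it.

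**Cycle length and anchor.** Section 4.1: "NL-201 will be administered as an IV infusion in 21-day cycles". Section 8.1.2 calls the first dose Day 1 and schedules later doses from that date.

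**DLT period (Section 6.2.1.3).** For Part 1 the text is "DLT must occur within Cycle 1 (< 21 days from first dose), or prior to completion of 21 days after first administration of NL-201". For Part 3 it is "The DLT window of observation will be during Cycle 1". Evaluability in Section 6.2.1.2 rests on "DLT-evaluable patients as defined by occurrence of DLT or completion of 21 days on study". Section 6.2.1.1 and Table 15 use the same 21 days. None of these sets a condition on the number of doses received.

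**Target quantity.** Sections 6.2.1.1, 6.2.1.2 and 9.4.2 define the MTD as the highest dose whose DLT probability during Cycle 1 is at most 33%.

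**The concern.** The matrices in Figures 5 and 6 are meant to score one regimen over one fixed period. If a second-cycle dose can be given before that period closes, some patients are scored on a heavier regimen than the one being judged. Inside the DLT period, Schedule A goes from one NL-201 dose to two, Schedule B from two to three, and pembrolizumab in Part 3 from 200 mg to 400 mg.

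Nothing in the DLT definitions removes the resulting events. Part 1 excludes only events plainly caused by progression or by something extraneous. Part 3 asks for relation to study treatment, not to a particular dose. The replacement rule in Section 4.1.3 does not address the case. What is at stake is a cohort held or de-escalated because of a Cycle 2 dose, which spends patients. Part 3 has a cap of 21 per schedule.

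**Working it through.** **1. Dates.** Inputs: first dose = Day 1 (Section 8.1.2), 21-day cycle (Section 4.1), window ±3 (Tables 1 and 2).

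Nominal Cycle 2 Day 1 = 1 + 21 = Day 22, so the window is Days 19 to 25. Day d is inside the Part 1 DLT period when d − 1 < 21.

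| Dosing day | Days since first dose | Inside the DLT period? | Days of overlap |
|---|---|---|---|
| 19 | 18 | yes | 3 |
| 20 | 19 | yes | 2 |
| 21 | 20 | yes | 1 |
| 22 | 21 | no | 0 |

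With a 0/+3 window the earliest dose is Day 22 and the overlap is zero.

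**2. The plan's matrices.** Both were rebuilt from the stated inputs: Beta(1,1) prior; target 33% with both epsilons 0.05 in Part 1; target 30% with both epsilons 0.03 in Part 3. The rule picks the largest unit probability mass, with DU when P(rate > target) > 0.95. The 0.95 cutoff is an assumption, because the documents do not state it. All 105 cells checked in each matrix (0–8 DLTs, n = 2–15) agree with Figures 5 and 6.

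**3. Effect of one added DLT (same in both figures).**
- n = 3: 0, 1, 2, 3 DLTs read E, S, D, DU. Each added DLT changes the action.
- n = 4: E, S, S, DU for 0–3. Going from 1 to 2 changes nothing.
- n = 6: E, E, S, S, DU for 0–4. Going from 0 to 1 or from 2 to 3 changes nothing; 1 to 2 moves E to S, and 3 to 4 moves S to DU.

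**4. Illustrative size.** The documents supply neither f, the share dosed early, nor q, the DLT risk of the extra dose inside the window. Both are assumptions here, as is a true Cycle 1 rate p = 0.20.

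Added DLTs per patient: a = f × q × (1 − p). Apparent rate = p + a. P(at least one added DLT in 3) = 1 − (1 − a)³. P(0/3) = (1 − p − a)³; with a = 0 this is 0.8³ = 0.512.

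| f | q | a | Apparent rate | P(≥1 added in 3) | P(0/3) |
|---|---|---|---|---|---|
| 0.10 | 0.02 | 0.0016 | 20.2% | 0.5% | 0.509 |
| 0.10 | 0.05 | 0.0040 | 20.4% | 1.2% | 0.504 |
| 0.10 | 0.10 | 0.0080 | 20.8% | 2.4% | 0.497 |
| 1/3 | 0.02 | 0.0053 | 20.5% | 1.6% | 0.502 |
| 1/3 | 0.05 | 0.0133 | 21.3% | 3.9% | 0.487 |
| 1/3 | 0.10 | 0.0267 | 22.7% | 7.8% | 0.462 |

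As an extreme, with every patient dosed early and q = 0.10, a = 0.08, the apparent rate is 28% and P(0/3) = 0.72³ = 0.373.

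**The case against.** **Part 1 already has a scoring rule.** This stands. A reader might infer that the plan leaves such an event unscored. It does not: the Part 1 text counts it, in the cautious direction. The fault is that the count then departs from the Cycle 1 quantity that defines the MTD.

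**The effect is small and its inputs are not in the documents.** This also stands. Section 6.2.1.4 says that in animals symptomatic toxicity peaks with the first dose and is attenuated afterwards. The early dose would normally go to someone who has just passed 18 to 20 days without a DLT. Both facts favour the low values of q. For pembrolizumab, Section 4.3 describes flat dose- and exposure-efficacy relationships over a wide range, and Section 8.5 sets overdose at 1000 mg, so a second 200 mg dose should not be dramatized.

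**The matrix only guides; the DMC decides.** True, and Section 6.4 has dose dates recorded, so an early dose can be seen. That lessens the consequence but does not remove the overlap.

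**The 48-hour observation rule cannot carry the argument for both parts.** The Summary of Changes justifies 48 hours by the early timing of most adverse events, but that rule belongs to Part 1. Section 4.1 uses 96 hours in Part 3, and even a Day 19 dose leaves only 72 hours inside the period.

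**Part 3 might be read as ending its window at the early dose.** A reader might infer shortened observation and unsafe escalation. The documents do not support this well: cycles are 21 days, and evaluability without a DLT requires 21 days on study. If that reading were used with all patients dosed early, and 2% or 5% of DLTs fell on Days 19–21, P(0/3) at a true 30% would rise only from 0.343 to 0.352 or 0.366.

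**Conclusion.** The overlap is real and follows from the dates alone: up to 3 of the 21 days, in both schedules, in Parts 1 and 3 without step-dosing. It can put a DLT caused by a Cycle 2 dose into the Cycle 1 count. The error is minor and conservative, and the likely harm is a false stay or de-escalation. Its frequency cannot be estimated from the documents, and the probabilities above depend on the assumed p, f and q.

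A reader might infer that one added DLT always changes the decision. That holds at n = 3; at larger n it often does not, and cohorts may be larger than 3.

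Under step-dosing the same overlap arises one stage later. The DLT period runs to 21 days after the target dose, and the next Day 1 visit (Cycle 3+ in Tables 3 and 4) carries ±3.

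**What to change.** For Parts 1 and 3 only:

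1. In Tables 1 and 2, set the Cycle 2 Day 1 window to 0/+3 by footnote. Table 4 already prints +3 at that visit.
2. In Tables 3 and 4, give the first Day 1 dose after the target dose no earlier than 21 days after the actual target-dose date. The actual date is needed because Section 8.1.2 schedules visits from Cycle 1 Day 1 and the target dose may itself have moved.
3. Align the early allowance in Table 7 and the pandemic row of Table 5 (±3 days for Day 1 dosing from Cycle 2 on) with this, for the visit that closes the DLT period.
4. Report any early dose that still occurs, now a deviation, to the DMC with its date.

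Do not make early-dosed, DLT-free patients non-evaluable and replace them. If a share d of DLT-free patients is removed, the observed rate is p / [p + (1 − p)(1 − d)]. At p = 0.20 and d = 0.05 this is 0.20 / 0.96 = 20.8%, against 20.2% under the current plan with f = q = 0.05. At d = 1/3 it is 27.3%, against 22.7% with q = 0.10. With d = f, such a rule is worse whenever q < p / [1 − (1 − p)f], a threshold that exceeds 20% at p = 0.20 for any f above zero. It would also use places under the Part 3 cap.

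The cost is a footnote in each of Tables 1–4 and a clause in each of Tables 5 and 7. Escalation sites lose early dosing at one visit; Parts 2 and 4 keep their windows.
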